Data on young adult-provider or dyad-provider communication and healthcare activities will be collected via MyChart messaging. All messages between young adults and providers or dyads and providers will be retrieved as transcripts for analysis. Patients and families at the MUSC Pediatric Sickle Cell clinic do not frequently use MyChart messaging to communicate with providers and instead send text messages. To encourage use of the more secure EHR portal (MyChart) – which has the added benefit of improved provider workflow – participants will be compensated for sending messages via MyChart. Participants will be compensated with \$2 for each message with a maximum possible compensation of \$20. The number of messages sent will be tallied at the end-of-intervention (12 weeks) and provided in the form of a gift card at that time.

Data on self-management behaviors, including monitoring and tracking symptoms and administering home medications and treatments will be collected via the app and stored in the secure app database. Specifically, we will collect data on the frequency symptoms are recorded (pain, fatigue, fever, etc.) and the frequency of accessing the pain graph component of the app. We will also collect data via the app on medication adherence and recorded treatments for symptoms (drinking water, heating pad, etc.). Data on clinic appointment attendance, ED visits, and details of appointments to assess acceptability of the intervention will be obtained during weekly phone checks. Also during weekly phone checks, adolescent participants will be asked 2 – 3 questions on functioning from the PedsQL Sickle Cell Disease Module and young adult participants will be asked 2 – 3 questions on functioning from the Adult Sickle Cell Quality of Life Measurement Information System (ASCQ-Me).

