**Post-intervention interviews:** Post-intervention interviews will be conducted by phone or in person (according to participant preference) with up to 15 adolescent/caregiver dyads and with up to 15 young adult participants to obtain more in-depth data on accessibility, usability, adherence to the intervention, and to explore how self-management behavior development influenced healthcare decision-making, such as actions taken to prevent pain. Participants who have completed the 12-week intervention period will be asked if they are interested in participating in an interview. We will use a purposeful sampling strategy to identify up to 15 dyads for interviews and will ask all young adult participants if they are interested in participating in an interview. Semi-structured interviews will be conducted using a qualitative descriptive approach, will last approximately 45 – 60 minutes, and will be conducted according to an interview guide with open-ended questions and prompts. The interviews will be audio recorded and transcribed by an outside agency with which MUSC has established a BAA for subsequent review and analysis. Dyads participating in key informant interviews will be compensated with a \$50 gift card.

In addition to conducting interviews with young adults and dyads, we will also conduct key informant interviews with up to 5 healthcare providers in person or by phone. Similarly to interviews with young adults and dyads, interviews with providers will be conducted to obtain more in-depth data on accessibility, usability, and adherence to the intervention. Semi-structured interviews will be conducted using a qualitative descriptive approach, will last approximately 45- 60 minutes, and will be conducted according to an interview guide with open-ended questions and prompts. Interviews will be audio recorded and transcribed by an outside agency with which MUSC has established a BAA

for subsequent review and analysis. Providers participating in key informant interviews will be compensated with a \$50 gift card.

Table 1: Measurement Framework

\*A = adolescents, CG = caregivers, HCP = healthcare providers

	Measures/instruments (number of items; Cronbach's alpha)	Sources	Time points
Demographic and clinical characteristics	Demographic survey	YA, A/CG report HCP report	Baseline
RE-AIM			

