## 11.0 Data Management

**Sex as a biological variable.** We recruit equal numbers of male and female adolescents and preliminarily explore for differences by sex in outcomes, such as acceptability, satisfaction, communication content, symptoms, quality of life, transition readiness, and utilization by conducting preliminary subgroup analyses in preparation for the subsequent larger trial.

**Feasibility processes.** Variables will include those pertaining to study procedures as well as participant variables. Specifically, 95% confidence intervals for proportions will be used to estimate dichotomous outcomes including the proportion of YA, A/CG who agree to participate out of the number approached, the proportion adherent to the intervention protocol, i.e., providing daily symptom monitoring/tracking, using the education component, responding to messaging, lost to follow up, etc. For the continuous feasibility measures (length of time spent in app components), frequency distributions and the median and mean responses with 95% confidence intervals will be obtained. Benchmarks for feasibility success are recruitment rate of at least 2 YA or A/CG per week, retention rates of 70%, use of at least one component of the app  $\geq 2$  days per week (adherence), and expressed satisfaction in key informant interviews (37).

**Outcome measures and estimates of variability.** Secondary aim outcomes variables will include measures of symptoms (pain, fatigue, depression, anxiety, sleep interference), quality of life, transition readiness, and utilization (number of appointments kept, number of ED visits). Demographic and clinical variables obtained at baseline will be described via measures of central tendency (mean, median), variability and frequency distributions as appropriate. Additionally, demographic and clinical characteristics for those who adhered to the study protocol versus those who did not adhere (non-adherers and drop outs) will be compared to better describe the study population. For continuous quality of life measures, the difference between pre-and post-intervention measurements will be estimated via 95% confidence intervals. To assess preliminary intervention effects, we will conduct repeated measures ANCOVA with variables in individual models adjusting for “dose” defined as number of times each portion of the app was accessed, total time spent in each portion of the app, number of days symptoms were recorded, and number of A/CG-provider messages.

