**13.0 Withdrawal of Subjects**

The PI may withdraw a participant from the study at any time if they decide it is in their best interest, if they do not follow the investigator's instructions, or if they fail to keep study visits. This may also occur if there is a protocol violation or early closure of the study.

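### The satisfaction benchmark rests on interviews to which completers of the 12 weeks are invited, so dyads who leave earlier fall outside it

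*Combined protocol and SAP*

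**What the plan says.** Section 11.0 (Feasibility processes) lists four benchmarks: a recruitment rate, "retention rates of 70" percent, a minimum frequency of app use, and "expressed satisfaction in key informant interviews". The last carries no threshold and no denominator.

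Section 10.0 (Post-intervention interviews) sets who is approached: "Participants who have completed the 12-week intervention period will be asked if they are interested in participating in an interview". Up to 15 dyads are then chosen purposefully. For young adults the team "will ask all young adult participants if they are interested in participating in an interview". The same section calls the dyad interviews key informant interviews, so these are the interviews the benchmark refers to. Table 1 times the semi-structured interview as post intervention.

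Providers are handled separately: "we will also conduct key informant interviews with up to 5 healthcare providers in person or by phone". No completion condition is attached to them.

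Section 13.0 allows the PI to remove participants for several reasons, including not following instructions "or if they fail to keep study visits".

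**The concern.** Satisfaction and acceptability are Aim 1 outcomes (section 1.0), and the interview benchmark is the only one of the four that concerns what participants thought of the program. The people invited are defined by having stayed. Those who disengaged and left, or were removed under section 13.0, are well placed to say what did not work, and the plan provides no interview in which they would say it.

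If leavers are less satisfied than stayers, the interviews would give a more favourable account than the enrolled families as a whole. Section 11.0 describes preparation for a larger trial, so that account could carry forward into its design. The Maintenance row of Table 1, also a primary aim, names the semi-structured interview as its only source, so interest in continuing would be judged on the same group.

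**Working it through.** The plan gives no figure to reproduce here. The check is a comparison of passages, followed by a count of how many people could be outside the interviews.

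**Who is inside the satisfaction benchmark**

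| Group | Invited under section 10.0? |
|---|---|
| Dyads who finish the 12 weeks | Yes, up to 15 by purposeful sampling |
| Dyads who leave before week 12 | No invitation planned |
| Young adults who finish | Yes, all asked |
| Young adults who leave before week 12 | Unclear: the completer sentence points to no, the all-young-adults sentence could mean yes |
| Stopped using the app but still enrolled | Possibly, since completion is not defined |
| Providers | Yes, up to 5, no completion rule |

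**Whether another source closes the gap**

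- Retention benchmark (11.0): counts leavers and does not record their opinion.
- Comparison of adherers with "non-adherers and drop outs" (11.0): covers demographic and clinical characteristics, not satisfaction.
- Weekly checks (10.0): "details of appointments to assess acceptability of the intervention will be obtained during weekly phone checks". These can record problems while a person is still enrolled.
- Table 1, Adoption row: satisfaction and reported problems, with weekly quality checks among the sources.
- Section F interim review: barriers to retention and user feedback.
- Integration matrix (11.0): compares the sources afterwards.

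Each may hold something about leavers, but section 11.0 makes none of them part of the satisfaction benchmark.

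**How many could be outside**

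Inputs: 30 dyads and 15 young adults (section 6.0), so 30 + 15 = 45 units; 70% retention (section 11.0). The time point for retention is not stated. I assume week 12, and that leaving the study counts as not retained.

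Formula: largest number outside = N − (smallest whole number at or above 0.70 × N).

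- Dyads: 0.70 × 30 = 21, so 30 − 21 = 9.
- Young adults: 0.70 × 15 = 10.5, so at least 11 are retained and 15 − 11 = 4 are outside.
- All units: 0.70 × 45 = 31.5, so at least 32 are retained and 45 − 32 = 13 are outside (9 + 4 gives the same). A loss of 14 would leave 31/45 = 68.9% and fail the benchmark.

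Range with better retention:

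| Retention at week 12 | Dyads outside (of 30) | Units outside (of 45) |
|---|---|---|
| 70% | 9 | 13 at most |
| 80% | 6 | 9 |
| 90% | 3 | 4 to 5 (45 × 0.10 = 4.5) |

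If retention is instead judged at the 3-month follow-up, 9 and 13 remain ceilings, but some of the permitted losses would fall after week 12 and the number outside could be smaller.

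**The case against.** Interviewing people who have been through the whole intervention is a defensible choice in a small single-group feasibility study. Leavers are not ignored: they count against retention, and the weekly checks, Table 1 data and interim review may capture their problems before they go. Many who leave may also be unreachable or may decline. All of this stands, and it limits the weight of the point. It does not put leavers' views into the benchmark that section 11.0 actually names.

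Two stronger readings are tempting, and the documents support neither.

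- A reader might infer that every patient and family interview is restricted to completers. Section 10.0 never says so in terms. The completer sentence could partly be about when the invitation is made, and the young adult sentence is wider. The completer reading is the more natural one under a post-intervention heading, but the secure scope is dyads who leave before week 12.
- A reader might put a percentage-point bias on satisfaction by assuming rates for completers and leavers. The plan estimates no such rate: dyads are sampled purposefully, the interviews go to content analysis, and the benchmark has no threshold. What may be missing is a perspective, and its size cannot be calculated.

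Completers' interviews can also reveal dissatisfaction. They cannot supply the views of those who left.

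**Conclusion.** The point holds in limited form. As written, the plan judges an Aim 1 outcome partly on interviews that dyads who leave before week 12 are not invited to give. Young adults who leave early are in the same position unless the wording is meant to include them. Provider interviews are unaffected. Under the week-12 assumption, up to 9 of 30 dyads, or 13 of 45 units, could be outside while retention is met.

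The direction of any distortion depends on leavers being less satisfied, which the plan does not say; if they are equally satisfied, the picture is not made more favourable. The undefined term for completion and the absence of a rule for judging the benchmark met are separate matters of clarity, and the finding does not rest on them. This is a cheap improvement, best made before the first interview, because leavers become harder to reach with time.

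**What to change.** In section 10.0 (Post-intervention interviews):

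- Keep the cap of 15 dyads, but also invite dyads and young adults who stopped early and still agree to be contacted.
- Include available early stoppers in the purposeful dyad sample.
- Reconcile the completer sentence with the one about asking all young adults.

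In section 11.0 (Feasibility processes):

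- Describe satisfaction separately for completers and early stoppers. A descriptive account fits the planned content analysis.
- If no early stopper is reached, state that the satisfaction benchmark applies to completers only.

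Cost: a protocol amendment, possibly consent wording for contact after stopping (the consent pages are not available to check), and modest staff time. The dyad gift-card maximum is unchanged at 15 × $50 = $750. Somewhat fewer completer dyads would be interviewed, and the result may be less favourable.

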## **6.0 Number of Subjects**

A total of 30 A/CG dyads (60 individuals), 15 young adults, and up to 5 healthcare provider participants will be consented into this study.

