## 10.0 Study Design / Methods

This single-group study will assess feasibility to test reach, efficacy, adoption, implementation, and maintenance of SMYLS using the RE-AIM framework (25) (Table 1) with 30 adolescents (A)/caregivers (CG), 15 young adults, and 5 healthcare providers involved with their care. YA and A/CG will be enrolled for a total of 6 months (12-week intervention with 3-month follow-up). Providers will be enrolled for as long as an adolescent under their care is currently enrolled ( $\geq 6$  months). We will obtain outcomes data on feasibility, self-management behaviors, and healthcare activities (primary aim), and transition readiness, symptoms, quality of life, and healthcare utilization (secondary aim). Measures include patient report via surveys, data recorded via the app, such as symptoms and app use, communication content from MyChart messaging, and in-depth data via key informant interviews.

Table 1 outlines the data to be collected and survey instruments to be administered at each of four data collection points: baseline, 6-weeks (mid intervention), 12-weeks (end of intervention), and 3-months post-intervention. Participants will be given the option of completing surveys in one of three ways: in person in a private room at the MUSC Pediatric Sickle Cell Clinic, by phone, or electronically through a link to REDCap. Estimated time for completion of surveys at each of the 4 visits is approximately 45 minutes. For in-person and phone data collection methods, all data will be recorded in REDCap by the PI or IRB-approved study personnel. Reimbursement to young adult and adolescent/caregiver dyads will be \$50 in the form of a gift card presented at each of the 4 data collection points. For A/CG participants, payments will be given to the caregiver; in the case of phone or electronic data collection, participants will be mailed the gift card by certified mail or will receive an electronic gift card via email.

Healthcare providers will complete a demographic survey in person or electronically at baseline. Subsequently, no surveys will be administered to healthcare providers.

Healthcare providers' study activities involve communicating with the young adults and adolescents/caregivers via MyChart.

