Reach: (primary aim) Sample Recruitment	Electronic log of sample characteristics; recruitment and enrollment activities	Recruitment tracking tools	Ongoing
Efficacy: Self-management outcomes (primary aim): Monitoring and tracking symptoms Attending clinic appointments Administering home medications and treatments Symptoms and health-related outcomes (secondary aim): Healthcare utilization (A only) Transition Readiness (A only) Pain (A only) Fatigue (A/CG) Depression (A/CG) Anxiety (A/CG) Sleep Interference (A/CG) Self-Efficacy (A/CG) Quality of Life (A/CG)	Pain and other symptom recording; treatments recorded; utilization reports 
 
PROMIS Pain Interference : Adult/Peds/parent proxy (8;0.87) (26)
 
PROMIS Fatigue SF : Adult (4; >0.9)(27); Peds/parent proxy (10 ; 0.87)(28)
 
PROMIS Emotional Distress: Depressive Symptoms SF : Adult (4; 0.97) (29); Peds/parent proxy (8; 0.94)(30)
 
PROMIS Emotional Distress: Anxiety SF Adult (4;0.97) (31); Peds/parent proxy (8; 0.83) (26)
 
PROMIS Self-Efficacy including general, manage daily activities, manage meds/treatment, manage symptoms: Adult (16; 0.97) (32)
 
Sickle Cell Self Efficacy Scale (9)
 
PROMIS Sleep Disturbance: Adult (4; 0.88)(33)
 
Adolescent Sleep Wake Scale (28; 0.86) (34)
 
Peds QL with Sickle Cell Disease Module (43; 0.95) (35)
 
Adult Sickle Cell Quality of Life Measurement Information System (30)
 
PROMIS Global Health Adult (10)
 
STARx (18; 0.8) (36)
 
Youth and Parent Sickle Cell Responsibility Scale
 
	YA, A/CG report Web-based application data capture Semi-structured interview Quality checks	Baseline, 6 weeks, 12 weeks, 3-months post intervention Ongoing Weekly
Adoption: (primary aim) Adherence (A/CG, HCP) Acceptability (A/CG, HCP) Education (A/CG) Symptom monitoring and tracking (A/CG) Communication (A/CG, HCP)	App overall use data; app component use data; satisfaction; reported problems; YA, A/CG-provider message content; MAUQ_SPA	Web-based application data capture Semi-structured interview Quality checks	Post intervention Ongoing Weekly

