**SECTION F. Interim Analysis**

This study aims to test the feasibility of a multi-component, technology-based intervention to promote self-management and symptom management among adolescents with sickle cell disease during the transition process from pediatric to adult care and parent-managed to adolescent self-managed care. To our knowledge, there are no similar interventions specifically designed for this patient population and purpose. As such, the BS will generate semi-annual qualitative interim analysis reports on a) adverse events; and b) data obtained during phone call and returned end-of-study surveys to understand issues related to the uptake, usability, and adoption of this platform among this population. We will evaluate the screening and enrollment procedures, barriers to participation and retention, including, safety, adherence, acceptability, technology problems encountered, if any, and user feedback from the participants and providers. This information gained from this structured process will be used to both guide the refinement of the current protocol and to inform the design of a larger efficacy trial. Interim analysis of outcome variables (transition readiness, adolescent pain, adolescent and caregiver fatigue and other symptoms, and quality of life) was not considered to avoid inexact inferences and increased chance of error due to few data points, as well as potential for bias if interim results were known to the investigators. Therefore, there are no planned stopping rules for this study.

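### Section 11.0 presents a dose-adjusted change over time in one group as an assessment of intervention effects, which this design cannot separate from other causes of change

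*Combined protocol and SAP*

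**What the plan says.** Section 10.0 sets the design: "This single-group study will assess feasibility to test reach, efficacy, adoption, implementation, and maintenance of SMYLS", within the RE-AIM framework. Section 6.0 gives the numbers: "A total of 30 A/CG dyads (60 individuals), 15 young adults, and up to 5 healthcare provider participants will be consented". Surveys are taken at baseline, 6 weeks, 12 weeks and 3 months after the intervention ends.

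The analysis is in section 11.0, in the paragraph on outcome measures and estimates of variability. For continuous quality of life measures, "the difference between pre-and post-intervention measurements will be estimated via 95% confidence intervals". It continues: "To assess preliminary intervention effects, we will conduct repeated measures ANCOVA", each model adjusting for a dose that includes "number of times each portion of the app was accessed, total time spent in each portion of the app", along with days of symptom recording and the number of messages between adolescent/caregiver dyads and providers.

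Section 1.0 limits the secondary aim for these outcomes to obtaining estimates of variability. No section names a comparator or a run-in period, and none cautions that change may have causes other than the app.

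**The concern.** An intervention effect is a contrast between what happened with the app and what would have happened without it. A single group supplies only the first half. The word preliminary warns that the estimate is imprecise; it does not warn that the change may not belong to the app.

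The documents themselves point to other sources of change:

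- Entry requires a self-reported history of pain at least monthly (section 5.0), and some participants are approached at clinic visits (section 8.0), so some regression to the mean is possible.
- Participants are 11 to 25 years old and are followed for 6 months, so transition readiness and self-efficacy may mature regardless of the app.
- Staff telephone participants weekly and pay $2 per MyChart message up to $20 (section 10.0). Staff also offer help with mental health resources when depression scores meet set criteria (section 14.0).
- The retention benchmark is 70% (section 11.0), so those measured late may differ from those who left.

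At stake is what the study may conclude about these outcomes, and what a later reader might carry into the design of the larger trial.

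**Working it through.** The plan contains no power, SD or effect-size figure to reproduce. The first step is therefore a reading of the text. The later steps are illustrations on assumed values.

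**1. Does the model identify an effect?** The time term estimates mean change in one group, that is, app effect plus all other change. One group gives one equation with two unknowns. Adjusting for dose does not add the missing contrast. Dose accrues after baseline and is not assigned. Much of it is symptom recording (section 3.0), so it may follow symptoms as well as influence them. Message counts are also affected by payment. A dose coefficient is an association with app use.

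**2. What the data can deliver.** The 95% half-width for a mean change, in SDs of the change, is t(0.975, n−1)/√n.

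| Group | n | Half-width |
|---|---|---|
| Adolescents, all | 30 | 0.37 |
| Adolescents, 70% retained | 21 | 0.46 |
| Young adults, all | 15 | 0.55 |
| Young adults, 70% retained | 10 | 0.72 |

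The groups are kept apart because Table 1 lists different adult and paediatric instruments.

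**3. How often drift alone would look like change.** Assume no app effect and a pre-post correlation of 0.5, so that the SD of change equals the SD of the measure. The chance that the 95% interval excludes zero comes from the noncentral t distribution with noncentrality drift × √n.

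| Drift (SD) | n = 21 | n = 30 |
|---|---|---|
| 0 | 0.050 | 0.050 |
| 0.1 | 0.072 | 0.083 |
| 0.2 | 0.141 | 0.185 |
| 0.3 | 0.258 | 0.355 |

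**4. A possible size for one source of drift.** Regression to the mean is entry shift × (1 − correlation) × SD. Assume SD 10, shift 0.3 to 0.5 SD and correlation 0.7 to 0.5:

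- low: 0.3 × 0.3 × 10 = 0.9 points
- high: 0.5 × 0.5 × 10 = 2.5 points

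**5. If the change were used to plan a trial.** Suppose the observed change is 4 points, with 80% power and two-sided 0.05. Then n per arm = 2 × (10 × (1.96 + 0.84)/4)², about 99. The standard error of the difference is 10 × √(2/99) = 1.42. Power is Φ(true effect/1.42 − 1.96).

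| Drift in the 4 points | True effect | Power |
|---|---|---|
| 0.9 | 3.1 | 59% |
| 2.0 | 2.0 | 29% |
| 2.5 | 1.5 | 18% |

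**The case against.** The strongest reply is that this is openly a feasibility study. Neither primary aim is an effect aim, the success benchmarks concern recruitment, retention, adherence and satisfaction, and no alpha or efficacy threshold is set. That stands, and it limits the point to one analysis sentence and how its result is described.

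A reader might infer that the protocol announces an efficacy result, because section 10.0 lists efficacy and Table 1 has a row beginning "Efficacy: Self-management outcomes (primary aim". The documents do not support this. Efficacy is a named RE-AIM dimension, the row also holds self-management behaviours and utilization, and section 10.0 speaks of assessing feasibility.

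A reader might also infer that the observed change will size the next trial, because Section F says information will "inform the design of a larger efficacy trial". There the information concerns screening, enrolment, barriers, retention, safety, adherence, acceptability, technology problems and user feedback. Section 11.0 links outcomes to the larger trial only through exploratory subgroup analyses by sex. No section says the change will be the planning effect.

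The illustration is also open to challenge, fairly. The entry criterion is a history of pain, not a cut-off on current severity, and the first recruitment route is telephoning earlier study participants, so regression to the mean is possible but not established. Nor should the assumed drift be compared with the 3.0 to 4.5 points in section 14.0: those concern depression scores and trigger an offer of help, whereas selection is on pain history.

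None of this supplies a comparator or a caution about attribution.

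**Conclusion.** The point holds for the section 11.0 sentence. In a single group, neither change over time nor a model adjusted for self-chosen, post-baseline app use can assess an intervention effect, and the stated aim for these outcomes does not call for one. This conclusion follows from the design and needs no assumed number.

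The consequence for the larger trial is conditional: planning could be misled if the change were used as an effect size. The power range of 59% to 18% rests on an assumed SD of 10, a 4-point observed change, an entry shift of 0.3 to 0.5 SD and a correlation of 0.5 to 0.7. It illustrates scale and does not predict a result. The stronger reading, that the plan claims efficacy and will size the next trial on it, goes beyond the text.

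**What to change.** In section 11.0:

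- Replace the stated purpose of the repeated measures ANCOVA with: *To describe within-person change from baseline*. Report mean change with 95% confidence intervals by participant group. The plan already does this in part for quality of life measures.
- Report dose results as associations with app use.
- Add: *The change cannot be attributed to the app and will not be used as the effect size of the larger trial, which may use the SDs and within-person correlations from this study.*

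The RE-AIM heading in Table 1 can stay, if wished with a note that the row is descriptive here.

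The cost is wording only. No endpoint, visit, participant or data item changes, and the estimates of variability that the secondary aim seeks are kept. What is given up is the possibility of describing the change as an effect of the app.

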**PROTOCOL TITLE: SMYLS: A Self-Management Program for Youth Living with Sickle Cell Disease**

**PRINCIPAL INVESTIGATOR: [name], RN**

## 1.0 Objectives / Specific Aims

### Primary Aims:

***Aim 1:** Assess feasibility of implementation processes among adolescents/caregivers, young adults, and providers including reach, enrollment, fidelity, adoption, acceptability, and satisfaction using the RE-AIM framework.*

***Aim 2:** Monitor health care activities that occur via adolescent/caregiver- or young adult-provider health communication and explore relationships between health care activities, such as provider screening, supporting, informing, and referring, and adolescent self-management behaviors, such as monitoring and tracking symptoms, attending clinic appointments, and administering home medications and treatments, and symptom outcomes.*

***Secondary Aim:** Obtain estimates of variability for measures of transition readiness, physical and psychological symptoms, healthcare utilization, and quality of life among adolescents, caregivers, and young adults.*

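### The repeated measures ANCOVA over four survey visits has no missing-data rule; fitted in its classical form it would lose at least 30% of units at the plan's own retention benchmark

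*Combined protocol and SAP*

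**What the plan says.** The paragraph on outcome measures in section 11.0 names one longitudinal model, for preliminary intervention effects: "we will conduct repeated measures ANCOVA with variables in individual models". It is run one variable at a time and adjusts for several measures of app use and messaging, which the plan calls dose. No estimation method, covariance structure, set of visits or missing-data rule is given.

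Section 10.0 sets the survey visits: "baseline, 6-weeks (mid intervention), 12-weeks (end of intervention), and 3-months post-intervention". Section 6.0 sets the sample: "A total of 30 A/CG dyads (60 individuals), 15 young adults, and up to 5 healthcare provider participants". The feasibility paragraph of section 11.0 lists "retention rates of 70" percent among its success benchmarks, without saying at which visit retention is counted.

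Section 11.0 also plans confidence intervals for the proportion lost to follow-up, a comparison of demographic and clinical characteristics between adherers and those who did not adhere or dropped out, and a separate 95% confidence interval for pre-post change in quality of life. The secondary aim in section 1.0 is worded as "Obtain estimates of variability for measures of transition readiness" and of other outcomes; it does not mention effects.

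**The concern.** The classical repeated measures fit needs a full row of outcomes for each person. Someone who answers at baseline, 6 weeks and 12 weeks but not at 3 months post-intervention contributes nothing. The plan accepts up to 30% loss as a successful study, so its outcome model should still work at that level of loss.

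Two things are at stake. Follow-up surveys already collected from people who later leave would be set aside. And if people who are getting worse are the ones who leave, the remaining group would appear to improve when the whole group did not. The study has a single group, so no control arm would reveal or offset this. Because the plan does not say which fit is meant, the choice could also be made after the data are seen.

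A lesser point is that the classical model assumes a simple covariance pattern, while the visits are unequally spaced (0, 6, 12 and about 24 to 25 weeks).

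**Working it through.** The plan states no analysable number and no power calculation, so there is no figure of its own to reproduce beyond the head count, which is right: 60 + 15 = 75 people, or 30 + 15 = 45 units (dyads plus young adults).

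**Inputs from the documents:** 45 units (section 6.0); 70% retention benchmark (section 11.0), read here as the share present at the last visit; four visits (section 10.0).

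**Inputs assumed:** the share *m* of retained units that skip a given follow-up survey, independently across visits. The documents give no value.

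**Step 1. Dropout alone.** Complete share = 0.70.
- 45 × 0.70 = 31.5 remain, 13.5 lost
- 30 dyads: 21 remain, 9 lost
- 15 young adults: 10.5 remain, 4.5 lost

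**Step 2. Skips at 6 and 12 weeks only.** Complete share = 0.70 × (1 − *m*)².

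| *m* | Share lost | Left of 45 |
|---|---|---|
| 0% | 30.0% | 31.5 |
| 5% | 36.8% | 28.4 |
| 10% | 43.3% | 25.5 |
| 15% | 49.4% | 22.8 |

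Losing one third requires *m* = 1 − √(0.6667/0.70) = 2.4%. Losing one half requires *m* = 1 − √(0.50/0.70) = 15.5%.

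**Step 3. Skips of 10% at all three follow-ups.** 0.70 × 0.9³ × 45 = 23.0. Final-visit completion is then 0.70 × 0.9 = 63%, so this is a harsher case than the benchmark itself.

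**Step 4. Data set aside.** Suppose loss runs at a constant rate to 70% at 24 weeks, with no skips. The shares present are then 0.915 at 6 weeks and 0.837 at 12 weeks. Visits observed per unit: 1 + 0.915 + 0.837 + 0.70 = 3.45. Visits used by a complete-case fit: 4 × 0.70 = 2.80. So 1 − 2.80/3.45 = 19% of collected visits go unused.

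**Step 5. Possible bias, by simulation.** Assumptions: 45 units, SD 10, visit correlations 0.5 to 0.7, higher scores worse, true change zero, and 30% leaving after week 6 with a probability that rises with worsening between baseline and week 6.
- Complete cases show a false 12-week change of about −1.0 to −1.4 points. A likelihood fit to all data shows 0.0 to about −0.2.
- With dropout at random plus 10% skips, the SD of the 12-week estimate is about 1.8 to 1.9 for complete cases and 1.55 for all data.

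For scale, section 14.0 uses a minimally important difference of 3.0 to 4.5 points on the depression t-score.

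**The case against.** The plan never says that only complete cases will be analysed. The label is also applied to mixed-model fits, and on that reading nobody with a usable visit is dropped. This stands: the loss is conditional on the classical fit. It does not remove the point, because the plan leaves open two readings that give different results.

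A reader might infer that 70% retention by itself discards a third to a half of the sample. It does not. It discards 30%, and anything beyond that rests on an assumed skip rate. A reader might also infer that the plan expects heavy missingness. It does not say so: 70% is a success threshold, and section 10.0 limits missed surveys by offering in-person, phone or electronic completion and a $50 payment at each visit, alongside weekly contact.

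A third tempting reading is that every standard deviation and change estimate passed to the larger trial would describe completers only. The documents do not support that. Nothing says the variability estimates come from the ANCOVA, baseline standard deviations do not depend on later dropout, and the quality-of-life intervals need two measurements, not four.

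The bias figures are smaller than the cited minimally important difference and depend on chosen inputs. The simulated dropout depends on observed worsening, which is the case a likelihood model handles well; dropout driven by unobserved worsening was not examined. The simulation also pools 45 units, although adolescents and adults complete different instruments for many outcomes. All of this limits the size of the consequence. The comparison of adherers with dropouts describes who left, but does not correct the outcome model.

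**Conclusion.** The point holds as a conditional one. The plan names a repeated measures ANCOVA over four visits and gives no missing-data method. If it is fitted in its classical form at 70% retention, at least 30% of units are lost (13 to 14 of 45). About 25 would remain with an assumed 10% skip rate at the two interim visits, and about 23 with that rate at all three follow-ups.

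The change estimates from this model would then describe completers, and would be biased if leaving is related to earlier worsening. The direction of that bias follows from the mechanism; its size cannot be known from the documents. What is affected is the analysis of preliminary effects, not the baseline variability estimates or the feasibility proportions. For a single-group feasibility study this is a change that should be made, because the better model uses data already being collected. It does not threaten the primary aims.

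**What to change.** In section 11.0, replace the repeated measures ANCOVA with a linear mixed model for repeated measures fitted by REML:

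- Treat visit as a category and include every participant with at least one outcome visit.
- Keep the planned dose covariates, and state over what period dose is counted for someone who leaves early.
- Fit the model separately for adolescents, caregivers and young adults.
- Use an unstructured covariance. With four visits it has 10 parameters, so name in advance a simpler structure for use if it does not converge, which is likely with 15 young adults.
- State the missing-at-random assumption.
- Report the number observed at each visit, and say at which visit the 70% retention benchmark is counted.
- Keep the complete-case result as a sensitivity check.

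The cost is a short rewrite of one paragraph and slightly more analysis work in standard software, with no new data or visits. The downsides are a possible covariance fallback in the young-adult group and reliance on missing at random, which the mixed model does not test.
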